6. STUDY ASSESSMENTS AND EVALUATIONS

6.1 Overview

All patients should visit the study center on the days specified within this protocol. The complete Schedule of Assessments for this study is presented in Appendix D.

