6.3 Central Nervous System (CNS) Prophylaxis

Patients with a history of CNS involvement of leukemia, with monocytic differentiation, or with a WBC >40,000 cells/ μ L should receive a lumbar puncture using either intrathecal (IT) methotrexate or cytarabine, following site-specific standard operating procedures during the first induction cycle of CPX-351 with quizartinib.

The CNS prophylaxis regimen may be modified by the attending physician in consultation with the PI as clinically indicated. No further IT chemotherapy is required in this study if there is no evidence of disease. However, additional administrations, per the treating physician or per institutional standard operating procedures, are permitted.

In patients who have CNS disease involvement, IT chemotherapy should continue every 4 days (\pm 1 day) until disease clearance, followed by every 7 days (\pm 2 days) for 2 additional administrations. Thereafter, administer IT chemotherapy every 28 days (\pm 7 days) for at least 12 cycles.

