6.4.1 Induction Phase

- Serum pregnancy test once per cycle during the induction phase

6.4.1.1 Cycle 1, Days 1, 3 and 5

- Physical examination and vital signs (Days 3 and 5)
- ECOG performance status (Days 3 and 5)
- AE monitoring
- Concomitant medication review
- CBC and clinical chemistry panel
- CPX-351 administration (Days 1, 3, and 5)

6.4.1.2 Cycle 1, Day 8

- Physical examination and vital signs
- ECOG performance status
- AE monitoring
- Concomitant medication review
- CBC and clinical chemistry panel

CONFIDENTIAL

STUDY DRUG: QUIZARTINIB
PROTOCOL DATE: 10 AUGUST 2020

DEVELOPMENT INNOVATIONS STUDY NUMBER: AML 48
VERSION 4.0

- ECG and QTc assessment
- Quizartinib daily on Days 8-21 (if QTcF \leq 450 msec)

6.4.1.3 **Cycle 1 Day 14**

- Physical examination and vital signs
- ECOG performance status
- AE monitoring
- Concomitant medication review
- CBC and clinical chemistry panel
- ECG and QTc assessment (if QTcF >470 msec, see Appendix F)

6.4.1.4 **Cycle 1 Day 21 (Response assessment)**

- Physical examination and vital signs
- ECOG performance status
- AE monitoring
- Concomitant medication review
- CBC and clinical chemistry panel
- BM biopsy and aspirate with FLT3 mutation testing via PCR
- ECG

6.4.1.5 **Cycle 1 Day 35 (\pm 7 days) (BM recovery)**

- Physical examination and vital signs
- ECOG performance status
- AE monitoring
- Concomitant medication review
- CBC and clinical chemistry panel
- BM biopsy and aspirate for MRD assessment via next-generation sequencing (NGS) and FLT3 mutation testing via PCR

6.4.1.6 **Cycle 2, Days 1 and 3 (re-induction, only applicable if patient achieves PR with recovery bone marrow after Cycle 1)**

- Physical examination and vital signs (Days 3 and 5)
- ECOG performance status (Days 3 and 5)
- AE monitoring
- Concomitant medication review
- CBC and clinical chemistry panels

CONFIDENTIAL

- CPX-351 administration (Days 1 and 3)

6.4.1.7 Cycle 2, Day 6

- Physical examination and vital signs
- ECOG performance status
- AE monitoring
- Concomitant medication review
- CBC and clinical chemistry panels
- ECG and QTcF assessment (if QTcF \leq 470 msec, resume quizartinib)
- Quizartinib (daily on Days 6-21, if QTcF \leq 470 msec)

6.4.1.8 Cycle 2 Day 14

- Physical examination and vital signs
- ECOG performance status
- AE monitoring
- Concomitant medication review
- CBC and clinical chemistry panel
- ECG and QTc assessment (if QTcF $>$ 470 msec, see Appendix F)

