Appendix D: Schedule of Assessments

ASSESSMENTS	Screening	Induction/Re-induction ^a								Consolidation ^b						At ~D30 interim ^c	Maintenance ^d		EOT	F/U	
Day		D1	D3	D5	D6 ⁿ	D8	D14	D21	D35	D1	D3	D6	D14	D21	D35		D1	D15			
Informed consent ^e	X																				
Inclusion/exclusion criteria	X																				
Medical history and demographics	X ^f																				
Physical examination, height (screening only), and weight ^g	X ^f		X	X	X ⁿ	X	X	X	X	X	X	X			X	X	X	X	X		
Vital signs ^h	X ^f		X	X	X ⁿ	X	X	X	X	X	X	X			X	X	X	X	X		
ECOG performance status	X ^f		X	X	X ⁿ	X	X	X	X	X	X	X			X	X	X	X	X		
12-lead electrocardiogram ^f	X ^f				X ⁿ	X	X	X			X	X	X	X			X	X	X		
TTE or MUGA scan	X ^f																				
Adverse event monitoring		X	X	X	X ⁿ	X	X	X	X	X	X	X			X	X	X	X	X		
Concomitant medication review	X	X	X	X	X ⁿ	X	X	X	X	X	X	X			X	X	X	X	X		
Lumbar puncture ⁱ		X																			

CONFIDENTIAL

STUDY DRUG: QUIZARTINIB
 PROTOCOL DATE: 10 AUGUST 2020

DEVELOPMENT INNOVATIONS STUDY NUMBER: AML 48
 VERSION 4.0

ASSESSMENTS	Screening	Induction/Re-induction ^a								Consolidation ^b						At ~D30 interim ^c	Maintenance ^d		EOT	F/U	
		D1	D3	D5	D6 ⁿ	D8	D14	D21	D35	D1	D3	D6	D14	D21	D35		D1	D15			
Central line placement (PICC or port)	Per institutional standards; placed prior to starting study treatment																				
CPX-351		Once daily (IV) on Days 1, 3 & 5. If re-induction is necessary administer on Days 1 & 3. During consolidation, administer on Days 1 & 3 for 2 cycles.																			
Quizartinib		Once daily (PO) Days 8-21 with induction. Days 6-21 with re-induction and/or consolidation(s).																Days 1-28 until PD			
Hematology panel	X ^f	X	X	X	X ⁿ	X	X	X	X	X	X	X			X	X	X	X	X		
Clinical chemistry panel	X ^f	X	X	X	X ⁿ	X	X	X	X	X	X	X			X	X	X	X	X		
Virus testing	X ^f																				
Urinalysis	X ^f																				
Serum Pregnancy Test ^{f,j}	X	X								X								Every 3 Cycles			
Bone marrow aspirate and biopsy (includes FLT3 mutation test via PCR) ^k	X							X	X						X	X ^k	Day 24 (± 3) at cycles 3, 6, 12 and 24				

CONFIDENTIAL

STUDY DRUG: QUIZARTINIB
 PROTOCOL DATE: 10 AUGUST 2020

DEVELOPMENT INNOVATIONS STUDY NUMBER: AML 48
 VERSION 4.0

ASSESSMENTS	Screening	Induction/Re-induction ^a								Consolidation ^b						At ~D30 interim ^c	Maintenance ^d		EOT	F/U
		D1	D3	D5	D6 ^a	D8	D14	D21	D35	D1	D3	D6	D14	D21	D35		D1	D15		
MRD analysis (FLT3 via NGS) ^l								X						X	X ^l	Day 24 (± 3) at cycles 3, 6, 12 and 24				

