- d **Maintenance:** Maintenance dosing of quizartinib will begin at 30 mg/day on Days 1-14, and if there are no toxicities and QTcF is maintained ≤450 msec, will increase to 60 mg/day on Day 15. The maintenance phase is a 28-day cycle beginning 7 days (± 7 days) after neutrophil recovery from the consolidation phase or induction phase. Patients will receive quizartinib once daily for a total of 24 cycles or until disease relapse. Patients who proceed to alloHCT or other CT intervention **after** consolidation will resume quizartinib maintenance 30-60 days from the intervention for a total of 24 cycles or until disease relapse. If the patient is on quizartinib prior to HCT or CT intervention, quizartinib should be discontinued 7 days prior if a conditioning therapy is utilized. If ≥2 CT interventions (e.g., repeat DLI) are planned after maintenance, a 28-day hold is acceptable, with resumption of quizartinib with the next cycle (see Section 5.2.4).
- e Informed consent must be obtained prior to the initiation of any screening test or procedure.

CONFIDENTIAL

STUDY DRUG: QUIZARTINIB
 PROTOCOL DATE: 10 AUGUST 2020

DEVELOPMENT INNOVATIONS STUDY NUMBER: AML 48
 VERSION 4.0

- f The screening medical history, physical examination, vital signs, ECOG performance status, and triplicate ECGs, TTE/MUGA, baseline signs and symptoms and safety laboratory tests (including pregnancy and virus testing [hepatitis serology (Hepatitis B surface antigen and antibody and Hepatitis C antibody), HIV-1, 2]) should be done following written consent and prior to initiation of therapy.
- g Physical examination will include measurements of height (screening only) and weight.
- h Vital signs will include resting heart rate, blood pressure, respiratory rate, and temperature.
- i Patients will receive a lumbar puncture during pre-transplant workup, per institutional practices and following site-specific standard operating procedures within the first 2 weeks on study treatment. No further intrathecal (IT) chemotherapy is required in this study if there is no evidence of disease. In patients who have CNS disease involvement, IT chemotherapy should continue every 4 days (± 1 day) until disease clearance, followed by every 7 days (± 2 days) for 2 additional administrations. Thereafter, administer IT chemotherapy every 28 days (± 7 days) for at least 12 cycles (see Section 6.3).

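### Appendix D schedules a lumbar puncture without the CNS-risk criteria of Section 6.3 and ties it to a transplant workup that Section 6.3 does not mention

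*Combined protocol and SAP*

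**What the plan says.** Section 6.3 (CNS Prophylaxis) names who should have the procedure: "Patients with a history of CNS involvement of leukemia, with monocytic differentiation, or with a WBC >40,000" cells/µL. It is given with IT methotrexate or cytarabine, and the timing is "during the first induction cycle of CPX-351 with quizartinib". The section allows judgment: "The CNS prophylaxis regimen may be modified by the attending physician in consultation with the PI as clinically indicated".

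Appendix D has a row labelled "Lumbar puncture", marked with footnote i, with a plain X under induction Day 1. Footnote i opens: "Patients will receive a lumbar puncture during pre-transplant workup, per institutional practices and following site-specific standard operating procedures within the first 2 weeks" of treatment. Its remaining sentences cover whether IT chemotherapy continues, and it closes "for at least 12 cycles (see Section 6.3").

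Section 6.1 gives the appendix its standing: "The complete Schedule of Assessments for this study is presented in Appendix D". The Section 6.4.1.1 list for Cycle 1 Days 1, 3 and 5 does not include a lumbar puncture. It ends with "CPX-351 administration (Days 1, 3, and 5").

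**The concern.** The two texts give different triggers for the same invasive procedure. Section 6.3 uses CNS risk. The schedule uses no stated risk condition and adds a transplant setting.

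Coordinators usually work from the schedule, so its wording largely decides what happens to a patient. Taken at face value, it sends a patient with no CNS risk factor for a lumbar puncture early in a myelosuppressive regimen. Section 7.5.2 itself lists hemorrhage and prolonged thrombocytopenia as CPX-351 risks.

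There is also a compliance problem. A patient with no risk criterion and no puncture is consistent with Section 6.3 but not with the words of footnote i. A monitor could not say whether that is a deviation.

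**Working it through.** No sample size, power or event count is involved, so the check sets the texts side by side.

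| Element | Section 6.3 | Appendix D row | Footnote i, first sentence |
|---|---|---|---|
| Who | Any of 3 risk criteria | No condition (0 of 3) | Patients, no condition (0 of 3) |
| Setting | CNS prophylaxis in induction | None stated | Pre-transplant workup |
| Strength | Should | X | Will, per institutional practices |
| IT drug | Methotrexate or cytarabine | Not stated | Not stated |
| Window | First induction cycle | Day 1 | First 2 weeks (Days 1–14) |

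**Step 1: criteria.** Footnote i mentions CNS disease once, to govern continued IT chemotherapy in patients who have it. That sentence does not decide who gets the initial puncture. Other Appendix D footnotes do state their conditions: j is for women of childbearing potential, k and l use an if-applicable qualifier, and n is for Cycle 2 of induction only. A site could therefore take the lack of a condition in footnote i at face value.

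**Step 2: which patients each text calls for.**

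| Patient | Section 6.3 | Footnote i, literal | Footnote i, transplant workup only |
|---|---|---|---|
| Criterion present, in workup | Yes | Yes | Yes |
| Criterion present, not in workup | Yes | Yes | Not called for |
| No criterion, in workup | Not called for | Yes | Yes |
| No criterion, not in workup | Not called for | Yes | Not called for |

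On either reading, footnote i differs from Section 6.3 in 2 of the 4 combinations. These are types of patient, not counts of patients.

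**Step 3: does the transplant setting fit the window?** Section 5.2 places transplant after a CR or PR from induction and/or consolidation. The first response marrow is at Day 21 ± 2 in Sections 5.2 and 6.5.11, so at the earliest on Day 21 − 2 = 19. Footnote k of Appendix D allows ± 7, giving Day 21 − 7 = 14. So the first response assessment falls after the two-week window or, at the widest tolerance, on its last day. Some sites may start a workup before response is known, but the phrase fits this schedule poorly.

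**Step 4: windows.** Day 1 lies within the first 2 weeks, which lie within the first induction cycle. With the 28-day cycle in the Figure 1 note, a puncture on Days 15–28 would meet Section 6.3 but not footnote i. The end of the cycle is not sharp, because Cycle 1 assessments run to Day 35 ± 7. This mismatch is secondary, and one common window removes it.

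**Step 5: other schedule text.** The Cycle 1 lists that fall in the first two weeks (Sections 6.4.1.1 to 6.4.1.3) do not name the procedure, so the visit lists do not settle the conflict.

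**The case against.** The strongest reply is that footnote i merely abridges Section 6.3. Its later sentences track Section 6.3 closely, it ends by pointing there, and its first sentence defers to institutional practice. Section 6.3 also gives the attending physician latitude. All of this stands and lowers the practical risk. It does not settle the matter, because the sentence that departs from Section 6.3 is the one about who receives the puncture, and a reader who follows the pointer finds a second trigger with no order of precedence.

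Four stronger readings are tempting, and the documents do not support them:

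- **A reader might infer that footnote i defines a rival population.** It says only that patients will receive the procedure and can be read two ways. That is ambiguity, and Step 3 makes the transplant-only reading the less plausible one.
- **A reader might infer that Section 6.3 forbids the procedure in other patients.** It says who should receive it and never says only, so a puncture outside the risk groups does not breach it.
- **A reader might infer that high-risk patients who are not transplant candidates lose prophylaxis.** Section 6.3 still covers them. Missing them would require a site to disregard body text that the footnote cites.
- **A reader might count every visit list in Sections 6.2 and 6.4 that omits the procedure.** Most cover re-induction, consolidation, maintenance or follow-up, where no initial puncture would be expected. Section 6.3 is itself a timed instruction within Section 6.

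**Conclusion.** The inconsistency is real and should be corrected at the next amendment. The row and the first sentence of footnote i carry none of the three Section 6.3 criteria and add a transplant setting that Section 6.3 lacks. The softening language does not say which rule governs. The main exposure is an invasive procedure in patients with no CNS risk factor, together with uncertainty over what counts as a deviation.

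The size cannot be given in patients: the documents state no prevalence for the risk criteria or for transplant candidacy. The response-rate test and the sample size are unaffected.

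The conclusion assumes that the schedule is read as written. It does not assume that the transplant phrase is a mistake. The documents do not show whether a separate puncture for transplant candidates was intended.

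**What to change.** - Mark the Appendix D row: *if applicable per Section 6.3*.
- Replace the first sentence of footnote i with: *Patients who meet the Section 6.3 criteria (history of CNS involvement, monocytic differentiation, or WBC >40,000 cells/µL) should receive a lumbar puncture with IT methotrexate or cytarabine within the first 2 weeks on study treatment, per institutional practices and site-specific standard operating procedures.*
- State the same two-week window in Section 6.3.
- Delete the reference to pre-transplant workup, unless the sponsor confirms that a separate puncture for transplant candidates is intended. In that case, add it as its own condition in both places.

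The cost is wording in one table row, one footnote and one sentence of Section 6.3, plus one question to the sponsor. No data collection or analysis changes, and no procedure is added unless the sponsor confirms the transplant condition.

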6.4.5 End of Treatment/Early Termination Visit

Patients will complete the study at the time of PD, if they withdraw consent, if they withdraw due to an AE, or at the time the study is terminated. If either study treatment or patients are discontinued, the reason will be recorded in the eCRF and source document. Patients who are removed from treatment for reasons other than death or disease progression (PD) are considered to be patients who have terminated early. Reasons for discontinuation include one of the following: AEs, protocol violation, patient withdraws consent, patient is lost to follow-up, administrative reasons (including study closure), death, or other. Patients who complete or discontinue from the study should have the following study completion/early withdrawal evaluations performed as soon as possible after the day of study completion/early withdrawal.

- Physical examination and vital signs

CONFIDENTIAL

STUDY DRUG: QUIZARTINIB
 PROTOCOL DATE: 10 AUGUST 2020

DEVELOPMENT INNOVATIONS STUDY NUMBER: AML 48
 VERSION 4.0

- ECOG performance status
- AE monitoring
- Concomitant medication review
- CBC and clinical chemistry panels
- BM biopsy and aspirate with FLT3 mutation testing, if applicable
- ECG and QTcF assessment, if applicable

Patients prematurely discontinuing from the study must be followed for AE and concomitant medication use for 30 days following the last administration of study drugs or until resolution/stabilization of an ongoing AE attributed to the medication.

Patients who discontinue from the study may be treated with other therapies at the discretion of the Investigator.

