The presence of the FLT3-ITD mutation will be detected using PCR from bone marrow aspiration samples collected with all planned BM samples. Next-generation sequencing of MRD by FLT3-ITD mutational analysis will be performed with all planned BM biopsies, excluding screening and the Day +21 induction response assessment. The presence of FLT3-ITD for inclusion is defined as positive if the PCR assay detects tandem duplication at 3% or higher.

6.5.8 **Response and Activity Assessments**

See Section 6.5.11 and Section 9.

6.5.9 **Adverse Event Assessments**

Information regarding the occurrence of AEs, including infections, will be collected from the time the patient signs the ICF throughout their participation in the study, including a period of 30 days after the last dose of study drug. Adverse event severity will be determined using the CTCAE Version 5.0 grading scale. See Section 11 for more details.

6.5.10 **Prior and Concomitant Medications**

All concomitant medications are to be collected and recorded from the time the patient signs the ICF and throughout the patient's participation in the study.

6.5.11 **Bone Marrow Aspirates and Biopsies**

Response assessment by BM biopsies and aspirates will be collected at Day 21 (± 2 days) of induction (and re-induction therapy, if applicable), as well as at the time of count recovery after CPX-351 + quizartinib, defined as obtaining a BM biopsy within 4 days of having an ANC $>500\mu\text{L}$ for ≥ 24 hours (at Day 35 [± 7 days] during induction and consolidation therapy). Bone marrow biopsies and aspirates will also be collected after Cycles 3, 6, 12, and 24 in the maintenance phase. Thereafter, assessment of disease status will be at the discretion of the primary treating hematologist/oncologist.

CONFIDENTIAL

All biopsies will include monitoring for FLT3 mutation by PCR. Additional studies, including fluorescence in situ hybridization (FISH), cytogenetics, and/or molecular analyses, should be obtained based upon known mutations at the discretion of the physician.

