9.6 Time-to-Progression (TTP)

Time-to-progression is defined as the number of days between diagnosis of relapse or refractory AML to disease progression, confirmed by bone marrow biopsy.

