9.7 Event-free Survival (EFS)

Event-free survival is calculated as the number of days from the first date of treatment to the first date of evidence of PD by BM biopsy/aspirate, or death, regardless of cause. Patients who are alive without a disease response assessment of relapsed disease will be censored at the last adequate disease assessment date. Patients without a disease response assessment will be censored at the first date of treatment. This calculation does not pertain to Long Term Follow-up data.

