- j A serum beta human chorionic gonadotropin pregnancy test must be done 72 hours prior to the start of treatment for women of child-bearing potential. Serum Pregnancy tests are also required prior to the start of each cycle during the induction and consolidation phases, during maintenance phase a serum pregnancy test will be obtained once every 3 cycles.
- k BM biopsies and aspirates will be collected at screening, Day 21 (± 7 days) during induction, and Day 35 (± 7 days) during both induction and consolidation phases (the time of count recovery after CPX-351 + quizartinib, defined as obtaining a BM biopsy within 4 days of having an ANC >500 for ≥ 24 hours) and at Day 28 (± 7 days) post-alloHCT or other CT intervention (if applicable). In the maintenance phase, BM biopsies and aspirates will also be collected on Day 24 (± 3 days) during cycles 3, 6, 12, and 24. Thereafter, assessment of disease status will be at the discretion of the haematologist/oncologist. All biopsies should include monitoring for FLT3 mutation by PCR (see Section 6.5.11).
- l MRD analyses with BM and aspirates and blood samples: Collect samples during BM recovery at the end of induction and consolidation phases (Cycle 1 Day 35 (± 7 days) and Cycle 2 Day 35 (± 7 days), 30 days post-alloHCT or other CT intervention (if applicable), and during the maintenance phase at Day 24 (± 3 days) Cycles 3, 6, 12, and 24.
- m Patients will be followed every 6 months during the 2 years after discontinuing study treatment for an underlying disease assessment (performed per Appendix E) and survival.
- n Cycle 2 of induction only.

CONFIDENTIAL

STUDY DRUG: QUIZARTINIB
PROTOCOL DATE: 10 AUGUST 2020

DEVELOPMENT INNOVATIONS STUDY NUMBER: AML 48
VERSION 4.0

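### A relapse stop without a marrow may be censored in EFS instead of counted: the end-of-treatment marrow in Section 6.4.5 is missing from the schedule, and Section 9.7 requires marrow evidence of progression

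*Combined protocol and SAP*

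**What the plan says.** **The end-of-treatment marrow.** Section 6.4.5 places the visit at progression or early stop: "Patients will complete the study at the time of PD, if they withdraw consent, if they withdraw due to an AE". Its list of procedures includes "BM biopsy and aspirate with FLT3 mutation testing, if applicable". When the marrow applies is not stated.

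**The schedule.** Section 6.1 says: "The complete Schedule of Assessments for this study is presented in Appendix D". In Appendix D, the marrow row for maintenance reads "Day 24 (± 3) at cycles 3, 6, 12 and 24", and its end-of-treatment cell is empty. Footnote k lists screening, Day 21, Day 35, the marrow after transplant or cellular therapy, and then maintenance marrows "during cycles 3, 6, 12, and 24. Thereafter, assessment of disease status will be at the discretion of the haematologist/oncologist". Section 6.5.11 has no end-of-treatment marrow either: "Bone marrow biopsies and aspirates will also be collected after Cycles 3, 6, 12, and 24 in the maintenance phase".

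**The endpoints.** Section 9.7 counts progression shown by marrow, or death from any cause. For the rest: "Patients who are alive without a disease response assessment of relapsed disease will be censored at the last adequate disease assessment date". It adds that long-term follow-up data are not used. Section 9.6 wants progression "confirmed by bone marrow biopsy". Section 9.8 defines recurrence by hematologic criteria and does not require a marrow. Section 10.4.2 reports Kaplan-Meier EFS rates at 6, 12 and 24 months.

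**The concern.** For a relapse between scheduled marrows, the marrow at the stop is the main on-study chance to record a progression event for EFS. It is also the one marrow that the schedule leaves out. A site working from Appendix D could stop a patient on circulating blasts and take no marrow. Long-term follow-up, which comes next, cannot restore the event because Section 9.7 excludes it.

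Patients censored in this way leave the risk set because they have just relapsed, so the censoring is informative and pushes EFS upward. The study has a single arm, so no control group shares the bias. The same relapse could also be an event for duration of response, since Section 9.5 counts relapse without naming a marrow, and a censoring for EFS.

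**Working it through.** **1. Is the empty cell a real omission?** The Appendix D end-of-treatment column is marked for the other Section 6.4.5 items: physical examination, vital signs, ECOG status, adverse events, concomitant medication, hematology, chemistry and ECG. The ECG carries the same conditional wording in Section 6.4.5 as the marrow, yet it is marked. Footnote k and Section 6.5.11 are prose lists, and both omit the marrow. A table-reading fault is therefore an unlikely explanation.

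**2. How far back can censoring go?** The plan gives no figure for this. With 28-day cycles and a marrow on Day 24, maintenance day = (cycle − 1) × 28 + 24.

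- Cycle 3: 2 × 28 + 24 = 80
- Cycle 6: 5 × 28 + 24 = 164
- Cycle 12: 11 × 28 + 24 = 332
- Cycle 24: 23 × 28 + 24 = 668

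The gaps are 84, 168 and 336 days (12, 24 and 48 weeks). With the ±3-day windows at both ends, the longest is 336 + 6 = 342 days.

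**3. Effect on EFS (illustration; every input is an assumption).** EFS is exponential with a true 12-month rate of 40%, so the 24-month rate is 0.40² = 16%. Deaths are 30% of events. The patient follows the full treatment path, with maintenance starting on Day 126 and marrows on Days 35, 77, 119, 205, 289, 457 and 793. A share q of relapses has no marrow at the stop and is censored at the previous scheduled marrow. Results are from a simulation of 400,000 patients.

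| Relapses that can lack a marrow | q | 12-month EFS (true 40%) | 24-month EFS (true 16%) |
|---|---|---|---|
| Maintenance only | 10% | 41% | 17% |
| Maintenance only | 25% | 44% | 20% |
| Maintenance only | 50% | 48% | 25% |
| All phases | 10% | 42% | 18% |
| All phases | 25% | 46% | 21% |
| All phases | 50% | 54% | 28% |

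A hand check for all phases: if missed relapses were censored on their own date, the event hazard would fall by the factor 1 − 0.7q, giving 0.40^(1 − 0.7q). That is 0.40^0.93 = 43%, 0.40^0.825 = 47% and 0.40^0.65 = 55%, close to the simulated values. So the bias comes mainly from losing the event, not from how far back the date moves.

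Varying the true 12-month rate (all phases, q = 10%, 25%, 50%): a true 20% reads 22%, 25% or 32%; a true 60% reads 62%, 65% or 71%. At q = 0 there is no bias.

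**4. Back-dating in the same model.** With all phases included, the median is 38 days. About 1.4% of missed relapses through Day 793 move back more than 300 days. Within maintenance the gaps are wider, so the shift there is longer.

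**5. Primary analysis.** The 13-of-30 rule reproduces (exact one-sided type I error 0.039, power 0.82 at 50%). ORR is read at the recovery assessment, where a marrow is scheduled, so nothing here changes it.

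**The case against.** A reader might infer that patients who relapse between scheduled marrows are, as a rule, censored up to 48 weeks back. The documents do not support that.

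- Section 6.4.5 is operative text and puts a marrow at the visit held at progression. Nothing forbids an unscheduled marrow, and Section 9.6 expects marrow confirmation. A site that follows these sections records the event on the right date. Only relapses called without a marrow are at risk.
- The discretion in footnote k most naturally begins after Cycle 24. It does not make marrows between scheduled dates discretionary. The evidence is the missing end-of-treatment entry.
- Section 9.7's censoring sentence speaks of an assessment of relapsed disease without naming a marrow, and leaves undefined what makes an assessment adequate. Read with Section 9.8, a relapse seen in blood is neither clearly an event nor clearly censored.
- Forty-eight weeks needs a relapse late in the Cycle 12 to 24 gap.
- The larger figures in the table assume that early relapses also lack marrows, although marrows are frequent before maintenance. About 32% of the modelled events by 24 months fall before Day 126. The model also ignores deaths after a missed relapse but before long-term follow-up, which Section 9.7 would count.

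All of this stands, and it makes the consequence conditional. It does not remove the conflict over whether the marrow is taken, or the silence on how a relapse without one is counted.

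**Conclusion.** The inconsistency is real, and its effect on EFS is possible but not certain. Where no marrow is taken at a relapse stop, Section 9.7 can be read to censor the patient at an earlier scheduled marrow, which biases EFS upward.

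On the assumptions shown, the 12-month bias from maintenance relapses is about 1 to 8 points as the missing share goes from 10% to 50%. It is 2 to 14 points if relapses in every phase can lack a marrow. The true share is not in the documents and could be near zero if sites follow Section 6.4.5.

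EFS is a secondary, descriptive endpoint. A reader might extend the point to time to progression, but Section 9.6 states no censoring rule, so any bias there is inference. The sample size and the primary ORR test are unaffected.

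**What to change.** 1. Reconcile Section 6.4.5, Section 6.5.11, the Appendix D end-of-treatment column and footnote k on the end-of-treatment marrow. Replace the open condition with a stated one, for example that relapse is suspected and not already marrow-confirmed.
2. Reconcile Sections 9.6 and 9.7 with Section 9.8, so that a relapse documented by hematologic criteria at the stop, with no marrow, counts as an EFS event on that date. The sponsor should specify the hematologic criterion. Define in Section 9.7 what makes a disease assessment adequate.

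The cost is amendment wording. The marrow is already in Section 6.4.5 and the end-of-treatment blood count is already scheduled. EFS may read slightly lower. The change should be made while patients are still on treatment, because a marrow that was not taken cannot be recovered at analysis.
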